7.2 SAMPLE SIZE CONSIDERATIONS

There are over 150,000 patients in the Cedars-Sinai Medical Delivery Network. Based on initial estimates from EIS, we expect blood pressure readings from at least 75,000 different patients and over 500,000 clinic visits annually, totally over 2.5 million blood pressure readings during the study period. This volume of longitudinal data will allow for development of the proposed measures (Aims 1-2) and to assess their validity and responsiveness (Aim 3A). About 75,000 number of records will be accessed and analyzed as a part of this research (Aim 1-2 and 3A). The home blood pressure cuff study (Aim 3B) is designed to provide pilot data for a proposed K23 application. Enrollment of 10 individuals into this study will demonstrate feasibility and data upon which to complete a larger grant application. Aims 4A and 4B represent components of a R21 grant proposal, with the stated funding purpose of developing pilot data to support a future R01 study.

Behavioral Economics to improve Antihypertensive Therapy Adherence (BETA)

NCT04029883

Statistical Analysis Plan

February 21, 2023

[name] MS
Director of Clinical Analytics

Cedars-Sinai Medical Center
Smidt Heart Institute

We will determine acceptability and feasibility from participants' program experience described above and the focus groups in Phase 3. To estimate preliminary efficacy, we will perform statistical analyses comparing group-level differences in the primary and secondary outcome measures. We will use an Analysis of Covariance (ANCOVA) framework to test for group differences in each outcome at 3-month intervals, controlling for the client characteristics that are found to differentiate the groups at baseline. For analyses of dichotomous variables, such as hypertension control, we will use a non-parametric McNemar's test and an analogous multiple logistic regression to control for covariates to assess group differences. In addition to static comparisons of group means for each outcome at 3-month intervals, we will take advantage of the longitudinal nature of the data by using repeated measures and time-series techniques. Specifically, a linear mixed model with repeated observations will be fit using maximum likelihood through 'xtmixed' in the software package Stata in order to study group-level temporal dynamics in daily measures of the primary and secondary outcomes.

Specific Aim 2a: The overall impact between the pooled (*Message* group + *Incentive* group) compared to the *Control* group will be evaluated using both: 1) the comparison of group means and 2) a repeated observation regression framework that controls for observable differences between study groups and the correlation between observations of the primary and secondary outcomes for the same individual over time.

Specific Aim 2b: The impact between the more intensive *Incentive* group compared to the lower-resource *Message* group will be evaluated using the same methods as above. Through this modeling framework we will utilize a range of variables. The independent variables in the above regression models will be used not only as control variables to improve efficiency but also to learn about the paths through which the intervention works and to identify subgroups that are likely to particularly benefit from the intervention. For example, by estimating regression models with and without measures of participants' intrinsic motivation as independent variables, we can study the mediating role of motivation on the formation of behavioral routines. The conceptual framework allows for additional mediators of behavior such as present bias, which may naturally hinder the capability of some participants to establish healthy routines. One additional method for testing this effect is to form an interaction between the present bias measure and the intervention indicator variable. With respect to the dependent variables, the primary and secondary outcomes are mean antihypertensive adherence and blood pressure control, with an exploratory focus on our quantified measure of adherence routinization. Continuous variables will be assessed for normality and transformed if needed. We will conduct analyses for the whole sample as well as separately by age and sex to better understand potential heterogeneous treatment effects. Logistic models will be estimated for binary outcome measures. We will also test whether routine adherence can be predicted based on observable characteristics; if so, in the subsequent R01 study the intervention may be targeted to those least likely to form healthy pill-taking routines on their own.

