The pilot RCT study would include 60 randomly selected hypertensive patients on hypertension treatment who may receive text message reminder and/or incentives, depending on the treatment group to which they are randomly assigned. Participants will be randomly assigned to one of three treatment groups: the control group (receives care as usual plus information on importance of establishing pill-taking routines), the message group (receives daily text messages for 3 months reinforcing information on importance of establishing pill-taking routines), or the incentive group (in addition to the same daily text messages as the message group, has a chance of winning small, intermittent rewards for taking medication in accordance with established pill-taking routine). The intervention period will last for 3 months and data monitoring will occur for an additional 6 months post-intervention totaling 9 months. Participants randomized into the incentive cohort will be eligible for a drawing only if they achieve greater than 80% medication adherence. The drawing will take place once a month for the first three months of participation with a chance to receive \$0, \$25, or \$50. Outcome measures include electronically measured medication adherence, hypertension control, adherence to established pill-taking routine, and feasibility and acceptability of intervention. We hypothesize that patients in the message and incentive groups will have higher medication adherence and hypertension control compared to the control group, and that patient in the incentive group will show greater adherence to established their pill-taking routine compared to the message and control groups.

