Finally, for Aim 4B, we will conduct unadjusted and then adjusted multivariate regression analyses assessing whether medication adherence, hypertension control, and adherence to pill-taking routine differ between treatment groups.

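### The SAP picks adjustment covariates by observed baseline differences between randomised arms, with no criterion, so the adjusted model is settled only after the arms are compared

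*SAP*

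**What the plan says.** Protocol 4.0 makes Aim 4B a randomised comparison: "Participants will be randomly assigned to one of three treatment groups". The SAP's opening paragraph tests each outcome by ANCOVA, "controlling for the client characteristics that are found to differentiate the groups at baseline". Under Specific Aim 2a, pooled intervention versus control is also analysed in a "repeated observation regression framework that controls for observable differences between study groups". Under Specific Aim 2b, Incentive versus Message "will be evaluated using the same methods as above". For dichotomous outcomes the SAP plans "an analogous multiple logistic regression to control for covariates to assess group differences" and names none of those covariates.

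Two other passages bear on the point. The SAP says the independent variables are "used not only as control variables to improve efficiency", which gives a purpose but no set. Protocol 7.1 says that "for Aim 4B, we will conduct unadjusted and then adjusted multivariate regression analyses", again without naming covariates. The SAP also states that "the primary and secondary outcomes are mean antihypertensive adherence and blood pressure control". Table 4 (Protocol 5.4) lists baseline blood pressure among the data collected, but no Aim 4B model commits to using it.

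**The concern.** When arms are formed by randomisation, a baseline difference between them is a chance event. Its size does not show whether the variable predicts adherence or blood pressure control, and it is prediction of outcome that makes adjustment worthwhile. A rule based on imbalance can admit irrelevant variables and leave out a strong predictor that happens to be balanced.

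The SAP also does not say what counts as a difference. It could be a p-value at some level, a standardised difference above some cut-off, or a judgement from the baseline table. Each reading gives a different model, chosen after the arms have been compared. The SAP does not say that outcomes guide the choice, but neither does it say that the choice is locked before outcomes are seen. At stake is how far the adjusted estimates can be relied on as pilot data for the later R01 (Protocol 7.2).

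**Working it through.** The documents state no alpha, power, effect size or selection threshold for Aim 4B, so there is no planned figure to reproduce. The text was checked first, and the consequences were then illustrated by calculation.

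**Is a criterion or list given anywhere?**

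| Place | Covariate rule | Threshold or fixed set |
|---|---|---|
| SAP, ANCOVA | those that differ between arms at baseline | none |
| SAP, Aim 2a repeated-observation model | observable differences between arms | none |
| SAP, Aim 2b | as Aim 2a | none |
| SAP, logistic model | unnamed covariates | none |
| Protocol 7.1, Aim 4B | unadjusted, then adjusted | none |
| Protocol 4.0, EMR adjustment variables | described for the retrospective work, not tied to Aim 4B | not applicable |
| Protocol 5.4, Table 4 | variables collected, not adjusters | not applicable |

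**Inputs.** From the documents: 60 patients (Protocol 3.1), three arms (4.0), and at least 14 baseline items in Table 4 (8 demographic or socioeconomic, 3 behavioural, 3 medical). Assumed: 20 per arm; a continuous outcome at one time point; 13 independent standard-normal candidates in the simulation; correlation r between a prognostic covariate and outcome; and four readings of the rule, namely p<0.05, p<0.20, largest standardised difference >0.1, and >0.2.

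**Step 1: chance of a difference.** For k independent items tested at level a, P(at least one) = 1 − (1 − a)^k. With k = 14: 1 − 0.95^14 = 51% and 1 − 0.80^14 = 96%. The expected numbers selected are 14 × 0.05 = 0.7 and 14 × 0.20 = 2.8.

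**Step 2: size of the model.** With 13 candidates the p-value readings should admit 13 × 0.05 = 0.65 and 13 × 0.20 = 2.6. For two arms of 20, a standardised difference has standard error √(1/20 + 1/20) = 0.316. So P(|d|>0.1) ≈ P(|Z|>0.316) = 0.75 and P(|d|>0.2) ≈ 0.53, that is about 9.8 and 6.9 covariates. Simulated means for the four readings, in the order above, were 0.6, 2.6, 12.3 and 10.5 (pooled, largest difference over three arms) and 0.7, 2.6, 9.8 and 6.9 (Aim 2b, 40 patients).

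**Step 3: dependence on the reading.** In each of 6,000 simulated trials, outcome was regressed on the treatment indicator plus the selected covariates under each reading. The span is the largest minus the smallest adjusted estimate, divided by the unadjusted standard error. For pooled versus control that error is √(1/20 + 1/40) = 0.274 outcome SDs (simulated 0.276). Cells show the median (90th percentile).

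| Comparison | Prognostic covariates | Four readings | p-value readings only |
|---|---|---|---|
| Pooled vs control | none | 0.41 (0.87) | 0.13 (0.46) |
| Pooled vs control | four at r=0.3 | 0.61 (1.22) | 0.20 (0.77) |
| Aim 2b | none | 0.52 (1.08) | 0.21 (0.65) |
| Aim 2b | four at r=0.3 | 0.69 (1.35) | 0.28 (0.87) |

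The last column comes from a separate run of 4,000 trials per case. In outcome units, the pooled four-reading medians are 0.41 × 0.274 = 0.11 SD and 0.61 × 0.274 = 0.17 SD.

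**Step 4: precision, pooled versus control.** Variance of the screened estimate divided by variance with the covariates fixed in advance, range over the four readings:

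| Truth | Fixed comparator | Variance ratio |
|---|---|---|
| one prognostic, r=0.3 | that covariate | 1.12–1.27 |
| one prognostic, r=0.5 | that covariate | 1.28–1.34 |
| one prognostic, r=0.7 | that covariate | 1.27–1.82 |
| four prognostic, r=0.3 | one of them | 0.89–1.07 |
| four prognostic, r=0.3 | all four | 1.23–1.47 |

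With one prognostic covariate, the Aim 2b ratios run from 1.17–1.45 at r=0.3 to 1.53–1.89 at r=0.7. At r=0, pre-specification gains nothing over the unadjusted analysis.

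**Step 5: type I error.** Rejection under the null, reading by reading, was 3.2–5.2% (pooled) and 2.4–5.0% (Aim 2b). If either the unadjusted or the screened test could count as success, it was 5.1–6.6% (separate run with 14 candidates and p-value cut-offs of 0.05, 0.10 and 0.20).

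**Step 6: blood pressure control.** Logistic likelihood-ratio test, 5,000 trials per case, supposing baseline pressure were screened at p<0.05. Power, screened / pre-specified:

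| Assumed % controlled | r=0 | r=0.3 | r=0.5 | r=0.7 |
|---|---|---|---|---|
| 40 vs 70 | 62/61% | 62/63% | 62/69% | 62/78% |
| 30 vs 50 | 32/33% | 32/34% | 31/37% | 32/45% |

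The repeated-observation model was not simulated.

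**The case against.** The strongest reply is that little of consequence rests on this rule. The trial is a small pilot estimating preliminary efficacy, unadjusted results are committed to in Protocol 7.1, and Aim 2a includes a plain comparison of means. The SAP's efficiency remark shows that prognostic adjustment is contemplated. All of that stands, and it limits the harm to the adjusted estimates.

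The four-reading span also leans on the two standardised-difference cut-offs, which admit nearly every candidate in the three-arm case. With p-value readings alone the medians fall to between about a third and two fifths of those figures, partly because p<0.05 selects nothing in about half of trials (0.95^13 = 51%). That is a fair point about size. The 90th percentiles remain at 0.46 to 0.87 standard errors, and nothing in the SAP says which reading applies.

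The precision gain requires naming the right covariates. For adherence, the documents describe no pre-randomisation electronic measure and no known predictor, so no size of gain is claimed there. For blood pressure control, the imbalance rule is attached to the ANCOVA sentence, not the logistic one. Step 6 is therefore conditional, and its gain at r=0.3 is only 1 to 2 points. These points narrow the benefit but do not supply the missing criterion.

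**Conclusion.** The concern holds. The SAP states a covariate rule that is unsuited to randomised arms, leaves its criterion open, and carries it into both Aim 2a and Aim 2b. No other passage fixes the set.

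The damage is moderate. No single reading inflates type I error, and the unadjusted comparison is unaffected. What suffers is the adjusted estimate. In the illustration its median dependence on the reading is 0.13 to 0.61 unadjusted standard errors for pooled versus control and 0.21 to 0.69 for Aim 2b, according to the readings allowed and whether covariates are prognostic. Its variance can exceed that of a well-chosen fixed model, by 12% to 27% in the case of one correctly named covariate at r=0.3. These sizes rest on equal allocation, 13 independent candidates and assumed correlations, none of which the documents give. The finding about the text does not depend on them. The plan should be changed, because the remedy is cheap and the estimates are meant to inform a larger trial.

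**What to change.** Replace the imbalance rule in the SAP with a short covariate set for each outcome, fixed before the arms are compared and used at every time point and for both Aim 2a and Aim 2b.

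- For blood pressure control, include baseline blood pressure in the logistic model and state the exact term in advance.
- For adherence, name a few Table 4 baseline variables that the team judges prognostic.
- Keep the unadjusted analysis from Protocol 7.1 and the exploratory motivation and present-bias models in the SAP.
- If adjustment for imbalanced variables is wanted, report it as a sensitivity analysis.

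The cost is SAP wording and a few degrees of freedom; no new data or visits are needed. If four fixed covariates turn out not to predict outcome, the simulated SD of the estimate rises from 0.276 to 0.287 (pooled) and from 0.315 to 0.334 (Aim 2b). In variance that is (0.287/0.276)² = 1.08 and (0.334/0.315)² = 1.12, which is why the set should be short.

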Aim 3B: Pilot study of the new time-to-control measure's responsiveness to more intensive blood pressure monitoring and intervention	
 1) Use of home blood pressure monitors linked the EMR will allow for weekly intervention by a clinical pharmacist, with titration of antihypertensive therapy, according the to 2017 ACC/AHA Hypertension Guidelines 2) The time-to-control period with will be shorter for those enrolled in the pilot study than those in the general population, not provided with home monitoring and weekly clinical pharmacist intervention
Aim 4A: Interview discussions to explore feasibility and acceptability intervention to increase blood pressure medication adherence	
 1) This is an exploratory aim, designed to inform Aim 4B. No a prior hypothesis.
Aim 4B: pilot study to measure the feasibility, acceptability, and efficacy of interventions designed to increase blood pressure medication adherence	
 1) Medication adherence and hypertension control will be greater among treatment groups compared to control group 2) Patients in the incentive group will demonstrate greater routinization compared to both the control group and the message group

For Aim 1, we will use these data to conduct descriptive analyses of rates of blood pressure control among patients with ambulatory care visits at Cedars-Sinai. Next, we will conduct multivariate regression models using blood pressure control as the outcome variable and various patient, physician and clinic characteristics as the independent variables. We will examine how results differ between the 2017 and JNC-7 guidelines.

For Aim 2, we will apply the new time-to-care measures and time-to-control measures to the same dataset. This will involve an iterative process of refinements as we discover issues that warrant the exclusion of certain blood pressure measurements, types of visits, or patient populations. The result will

be both refined measures and descriptive data on the time-to-care and time-to-control for both undiagnosed and uncontrolled hypertension.

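### The SAP names McNemar's test, a paired-data test, for differences in hypertension control between independently randomised arms

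*SAP*

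**What the plan says.** The SAP's general methods paragraph covers binary outcomes in one sentence. It opens "For analyses of dichotomous variables, such as hypertension control" and continues "we will use a non-parametric McNemar's test and an analogous multiple logistic regression to control for covariates to assess group differences". The stated purpose is therefore a comparison of groups.

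The groups are the Aim 4B arms. Protocol section 4.0 says "Participants will be randomly assigned to one of three treatment groups" (control, message, incentive), and section 3.5 confirms that assignment is random. Neither document describes matching, pairing or crossover. The hypothesis in protocol section 7.1 is between arms: "Medication adherence and hypertension control will be greater among treatment groups compared to control group".

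The SAP has two contrasts, both between different people:

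- **Specific Aim 2a:** Message and Incentive pooled, against Control. The methods listed are "the comparison of group means and 2) a repeated observation regression framework that controls for observable differences between study groups". McNemar's test is not named in that list.
- **Specific Aim 2b:** Incentive against Message, which "will be evaluated using the same methods as above".

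Two other places plan methods that do suit independent arms. The SAP says under Specific Aim 2b: "Logistic models will be estimated for binary outcome measures". Protocol section 7.1 plans "unadjusted and then adjusted multivariate regression analyses assessing whether medication adherence, hypertension control" and routine adherence differ between the groups.

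**The concern.** McNemar's test uses only discordant pairs: subjects, or matched pairs, whose two binary readings differ. It needs a real link between the two readings. Patients in different randomised arms have no such link, so the named test does not answer the question set for it.

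An analyst who follows the sentence literally has two routes, and neither gives a valid test of the group difference:

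- **Pair unrelated patients across arms.** The p-value then depends on which pairing was chosen. If allocation is equal, contrast 2a is 40 v 20, and 1:1 pairing also drops 20 treated patients.
- **Pair each patient's baseline and follow-up readings within an arm.** The trial has repeated readings, so this is the more natural misuse. It tests change over time. A significant result in one arm and not in another could then be presented as a treatment effect.

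Blood pressure control is the secondary outcome in the SAP and half of the first Aim 4B hypothesis. In the quoted sentence, the logistic model is the covariate-adjusted analysis, so McNemar's test is the only unadjusted test that the SAP names specifically for binary outcomes.

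**Working it through.** The documents give no alpha, power, effect size or control rate for Aim 4B, so there is no planned figure to reproduce. The check illustrates what the named test would do.

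**Inputs**

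- 60 patients (protocol section 3.1) in three arms (section 4.0).
- Assumed: 20 per arm and two-sided 0.05. All control rates are illustrative.

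**1. Contrast 2b, 20 v 20, arbitrary pairing**

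Let a and c be the numbers controlled in the two arms, and k the number of pairs with both controlled. The discordant counts are a − k and c − k. The exact p is the two-sided binomial test of a − k out of a + c − 2k at 0.5. Under random pairing, k is hypergeometric (20, a, c).

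For 14/20 v 7/20:

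| k | discordant | exact p | share of pairings |
|---|---|---|---|
| 1 | 13 v 6 | 0.167 | 0.0002 |
| 2 | 12 v 5 | 0.143 | 0.007 |
| 3 | 11 v 4 | 0.118 | 0.070 |
| 4 | 10 v 3 | 0.092 | 0.258 |
| 5 | 9 v 2 | 0.065 | 0.387 |
| 6 | 8 v 1 | 0.039 | 0.232 |
| 7 | 7 v 0 | 0.016 | 0.044 |

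The share below 0.05 is 0.232 + 0.044 = 0.28. The same method gives:

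| Result | McNemar p over all pairings | Fisher p |
|---|---|---|
| 12/20 v 9/20 | 0.25 to 0.65 | 0.53 |
| 14/20 v 7/20 | 0.016 to 0.167 | 0.056 |
| 17/20 v 7/20 | 0.002 to 0.021 | 0.003 |

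Pairing changes the side of 0.05 only in the borderline case, but the p-value is arbitrary in all three.

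**2. Contrast 2a, 40 v 20, arbitrary pairing**

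Take 28/40 v 7/20. The number controlled among the 20 treated patients kept is hypergeometric (40, 28, 20); these are then paired as in step 1. The central 95% of selections and pairings give p from 0.004 to 0.34, and about 60% give p above 0.05. Fisher's exact test on all 60 gives 0.013.

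**3. Power and type I error, between arms**

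| Contrast | True control | McNemar, 20 arbitrary pairs | Fisher, all patients |
|---|---|---|---|
| 2a | 70% v 35% | 46% | 68% |
| 2a | 70% v 50% | 15% | 29% |
| 2b | 70% v 35% | 46% | 47% |

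With equal true rates (20%, 30%, 50%, 65% and 70%), McNemar's test on 20 arbitrary pairs rejects 1.5% to 2.3% of the time. It is conservative, not liberal.

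**4. Within-arm use**

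Assume all 20 patients in an arm are uncontrolled at baseline. Protocol section 2.0 describes participants this way, but the Aim 4B eligibility criteria do not require it. Change can then go only one way. The test rejects once 6 patients become controlled, since 2 × 0.5⁶ = 0.031, while 5 gives 2 × 0.5⁵ = 0.0625. If every arm has the same follow-up control rate p, so that treatment has no effect, the rejection probability in one arm is P(X ≥ 6) with X binomial (20, p):

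| p | 20% | 30% | 40% | 50% |
|---|---|---|---|---|
| P(reject) | 0.196 | 0.584 | 0.874 | 0.979 |

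These are correct rejections of no change over time. They carry no information about a difference between arms.

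**The case against.** The strongest reply is that little is lost. The same SAP sentence also plans logistic regression, the SAP repeats this under Specific Aim 2b, and protocol section 7.1 plans regression both unadjusted and adjusted. An analyst could report those and never run McNemar's test. The method list for 2a does not name it, so its application there is inferred from the general paragraph. This is a pilot meant to inform a later grant application (protocol section 7.2), and no decision rule rests on this p-value. No one is likely to invent pairs across arms, and even then type I error is not inflated and contrast 2b loses almost no power.

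All of that stands, and it limits the consequence. It does not make the named test right: the sentence says the purpose is to assess group differences. The within-person reading does not rescue it either, because that answers a different question and carries the larger risk of misreading (step 4 above). The two documents also differ on the unadjusted method, since the protocol plans unadjusted regression and does not mention McNemar's test.

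**Conclusion.** The concern holds. McNemar's test is wrong for the stated purpose; the logistic regression beside it suits the design. It should be fixed, but the comparison of hypertension control is not lost.

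The risk is a McNemar p-value being reported as evidence of a group difference. Between arms, that p-value is arbitrary (0.016 to 0.167 for one and the same 14/20 v 7/20 result), and in 2a it costs power (46% against 68% at 70% v 35%). Within arms, it may be significant with no treatment effect (58% of the time at 30% control, if all start uncontrolled).

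The test-choice error depends on none of the assumed figures. It rests on random assignment to separate arms and on no matching being described. The sizes do depend on 20 per arm, 1:1 pairing, two-sided 0.05 and the illustrative control rates. The verdict covers this one SAP sentence and does not clear the rest of the SAP; in particular, using a linear mixed model for a binary secondary outcome is a separate question.

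**What to change.** In the SAP sentence on dichotomous variables:

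1. Replace McNemar's test with one independent-groups test, named in advance, for the unadjusted comparison. Either Fisher's exact test or the unadjusted logistic regression already in protocol section 7.1 would serve. I would choose Fisher's exact test, because the Wald approximation is rough at about 20 per arm. The choice must be made beforehand because the two can disagree: for 14/20 v 7/20, the log odds ratio is ln(14/6) − ln(7/13) = 1.466 with standard error √(1/14 + 1/6 + 1/7 + 1/13) = 0.677, so z = 2.17 and Wald p = 0.030, against 0.056 for Fisher.
2. Keep the adjusted logistic regression, but drop the word that calls it analogous. The regression counterpart of McNemar's test is conditional logistic regression, which is not wanted here.
3. State that both analyses apply to contrasts 2a and 2b.
4. If McNemar's test is kept at all, label it a within-arm description of change from baseline, not a test of group difference.

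The cost is a few lines of SAP text, with no new data and no more patients.

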3.0 STUDY POPULATION

3.1 SELECTION OF THE STUDY POPULATION

1. For Aims 1, 2 and 3A, data for patients will be obtained from the Cedars-Sinai electronic medical record.
2. For Aim 3B, a sample of 10 patients seen in the Hypertension Center or Women’s Heart Center clinic, who meet the pre-defined criteria for uncontrolled hypertension at the time of data procurement, will be selected.
3. For Aim 4A, a sample of 20 patients seen in the Hypertension Center or Women’s Heart Center as well as 7 medical providers will be selected to inclusion in interview discussions.
4. For Aim 4B, a sample of 60 patients hypertensive patients taking antihypertension medications will be selected.

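### Logistic regression for blood pressure control has no fixed covariate set in about 40 to 60 patients, so its adjusted odds ratio may be exaggerated and imprecise if several terms enter

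*SAP*

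**What the plan says.** The first analysis paragraph of the SAP plans ANCOVA, "controlling for the client characteristics that are found to differentiate the groups at baseline". For dichotomous variables, with hypertension control as the example, it then names McNemar's test and "an analogous multiple logistic regression to control for covariates to assess group differences". On the natural reading, the covariate rule stated for ANCOVA carries over to this model.

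The paragraph on Specific Aim 2b adds "Through this modeling framework we will utilize a range of variables" and "Logistic models will be estimated for binary outcome measures". It also offers a treatment interaction and plans separate analyses by age and by sex. Its contrast is "The impact between the more intensive *Incentive* group compared to the lower-resource *Message* group", to be analysed by the methods already given for Aim 2a (pooled intervention groups against control).

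Protocol section 4.0 gives the size, "The pilot RCT study would include 60 randomly selected hypertensive patients", and the design, "Participants will be randomly assigned to one of three treatment groups", without an allocation ratio. Table 4 (section 5.4) lists baseline blood pressure, eight demographic and socioeconomic items, and further behavioural, medical and structural-barrier items. Section 7.2 gives no power, effect size or control rate for Aim 4B.

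Neither document limits the number of covariates in the logistic model, names a penalised or exact method, or says what happens if the fit does not converge.

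**The concern.** Maximum-likelihood logistic regression is biased away from the null when there are few outcomes per coefficient. The bias grows as terms are added, and at the extreme the data separate and no finite estimate exists. Here the sample is small and the number of terms is left to whatever imbalance is seen at baseline. Several of the Table 4 items are categorical (education, employment, insurance type, marital status, housing), so a single item can use more than one coefficient.

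The odds ratio for control is a planned secondary result of a pilot whose stated purpose is to supply data for a future R01. An exaggerated or very unstable estimate would pass into the planning of that study.

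**Working it through.** The plan gives no figure to reproduce: 60 is not derived from any stated input. The check is whether the planned model estimates a known odds ratio (OR) correctly at this size.

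**Inputs.** From the documents: 60 patients, three arms. Assumed: 20 per arm, so Aim 2a is 40 v 20 and Aim 2b is 20 v 20 in a two-arm fit. Also assumed are the control rate (the only anchor is the 50% national uncontrolled rate in protocol section 7.1), the true OR, the number of covariates and their strength.

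**Outcomes per coefficient.** With half controlled, there are 20 events in 40 patients and 30 in 60. Counting treatment plus k covariates:
- 40 patients: 20/5 = 4.0 (k = 4) and 20/9 = 2.2 (k = 8)
- 60 patients: 30/5 = 6.0 and 30/9 = 3.3

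**Simulation 1, true OR 2.** Logit = ln(2) × (treatment − 0.5) + 0.8·Z1 + 0.3·(sum of the other Z), independent standard normal covariates, about 50% controlled, 1,500 trials per setting. Ordinary maximum likelihood is compared with Firth, which maximises log-likelihood + ½ ln|information|. Ranges are over repeated runs.

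| Patients | Covariates | Ordinary, median OR | Firth, median OR |
|---|---|---|---|
| 40 | 0 | 1.91 | not run |
| 60 | 0 | 2.03 | not run |
| 40 or 60 | 1 | 1.99 to 2.16 | 1.88 to 2.05 |
| 40 | 2 | 2.17 | not run |
| 60 | 2 | 2.19 | not run |
| 40 | 4 | 2.27 to 2.44 | 1.93 to 2.07 |
| 40 | 8 | 2.67 to 2.76 | 1.93 to 2.07 |
| 60 | 4 | 2.11 to 2.17 | 1.93 to 2.07 |
| 60 | 8 | 2.33 to 2.38 | 1.93 to 2.07 |

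On the log scale, a median of 2.3 is ln 2.3/ln 2 − 1 = 0.833/0.693 − 1 = +20%, and 2.7 is 0.993/0.693 − 1 = +43%. At 40 patients the root mean square error of the log OR is 1.00 (4 covariates) and 1.88 (8) for the ordinary fit, against 0.77 and 0.95 for Firth.

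**Simulation 2, true OR 3.** A different data model: half of the covariates binary, comparator-arm control rate 50%, 1,500 trials per setting. The table gives the geometric-mean OR from the ordinary fit. Bias = ln(OR)/ln 3 − 1; for example, ln 3.92/ln 3 − 1 = 1.366/1.099 − 1 = +24%. The benchmark is the true conditional OR, so non-collapsibility is not counted as bias.

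| Covariates | 0 | 2 | 4 | 6 | 10 |
|---|---|---|---|---|---|
| 60 patients, OR | 3.07 | 3.32 | 3.52 | 3.76 | 4.47 |
| Bias in log OR | +2% | +9% | +15% | +21% | +36% |
| 40 patients, OR | 3.18 | 3.54 | 3.92 | 4.65 | 6.47 |
| Bias in log OR | +5% | +15% | +24% | +40% | +70% |

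Over all settings tried (comparator rates 30%, 50% and 70%), Firth gave 2.91 to 3.09 with 60 patients and 2.88 to 3.28 with 40.

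**No true effect.** In simulation 2 the geometric-mean OR is 0.97 to 1.02 and type I error is 4 to 7% with 40 to 60 patients. Only the spread grows: at 40 patients the SD of the log OR rises from 0.67 to 1.44 as covariates are added. In simulation 1 with 40 patients and 8 covariates, 28% of ordinary estimates were at least 4 or at most 0.25, against 11% with Firth.

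**No finite fit.**
- Simulation 1, 40 patients: 0.1 to 0.4% of trials with 4 covariates, 3.4% to about 5% with 8. With 60 patients: none seen.
- Simulation 2, comparator rate 50%: 0.1% or less with 60 patients; 0.3% to 7.6% with 40 as covariates go from 0 to 10.
- Simulation 2, comparator rate 70%: 0.4 to 10% with 60 patients and 6 to 37% with 40.
- Age or sex halves, 50%, 4 covariates: 7% with 30 patients and 26% with 20.

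**The case against.** The strongest reply is that the covariate load is assumed. In a randomised trial the characteristics that differ at baseline may be few or none, and with up to two covariates the ordinary fit is close to the truth. This stands, and it makes the point conditional. It does not remove it, because the SAP leaves the number open and Table 4 offers many candidates.

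A reader might infer that intrinsic motivation and present bias will be loaded into the model for blood pressure control. The SAP does not say so. Its examples tie both to the formation of routines, which it calls exploratory, and it speaks of fitting models with and without motivation.

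A reader might also blame the method for every extreme estimate. At a true OR of 2 with 40 patients, the ordinary fit gave an OR of 4 or more in 28 to 29% of trials (4 covariates) and 38 to 40% (8). But Firth gave 18 to 20%, and the ordinary fit with no covariates gave 17%. Much of this is sampling noise that no estimator removes.

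The reply that Firth adds little once the model has a single covariate is also fair. Its main use there is protection against separation. Finally, that the fit is unpenalised is inferred: the SAP names maximum likelihood only for the linear mixed model. Plain logistic regression normally means maximum likelihood, so the inference is reasonable.

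**Conclusion.** The point holds in conditional form. As written, the SAP allows an adjusted odds ratio for control that may be exaggerated and imprecise if there is a true effect and about four or more covariate terms enter. The bias in the log odds ratio at a true OR of 3 is about 15 to 36% with 60 patients and 24 to 70% with 40, for 4 to 10 covariates.

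The documents do not support the stronger readings that the plan will overstate the odds ratio whatever happens, or that the full-sample models are likely to fail. With up to two covariates the bias is 2 to 9% (60 patients) or 5 to 15% (40), and under no effect there is no directional bias. Failure to converge is rare in the full contrasts near 50% control. It matters at higher control rates, with many terms in 40 patients, or in the age and sex subsets.

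The sizes rest on equal allocation, a two-arm fit for Aim 2b, and the assumed control rate, true OR and covariate strengths. Because this is a secondary outcome of a pilot and the remedy is cheap, the change is advisable rather than essential.

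**What to change.** For hypertension control, drop covariate selection by observed imbalance. Prespecify one treatment-effect model: treatment plus baseline blood pressure, which Table 4 already collects, fitted by Firth-penalised logistic regression with profile-likelihood confidence intervals. Say which baseline reading enters (one term for systolic alone, two if diastolic is added) and whether Aim 2b is fitted to two arms or within a three-arm model. Label as exploratory any model of control with more variables, a treatment interaction, or age or sex subsets.

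The cost is SAP wording and a standard routine, with no new data, visits or patients. The downside is slight shrinkage of the odds ratio. With one covariate, most of the gain comes from fixing the covariate set; Firth adds only a little beyond its protection against separation. The use of McNemar's test in the same SAP sentence is a separate question and is not settled by this change.
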